Official Title: Preliminary Studies to Test the Effects of Ambulatory Voice Biofeedback: Study 2

NCT Number: 03416868

Date: August 14th, 2024

Study Protocol:

Study Two will involve 48 total patients (20 with phonotraumatic VH and 20 with non-phonotraumatic VH + potential 20% drop out rate), each handled as a single subject design to test if large changes in voicing occur during AVB (acquisition) and the days post-AVB (retention). This experimental design is best suited for the study since (1) AVB can only be effective via an individualized approach to therapy and (2) we aim to demonstrate improvement with AVB across subjects who will have different measures as biofeedback targets. To be offered participation, each patient must successfully complete approximately one week of pre-therapy ambulatory data (acquired from protocol 2011P002376) and will need to demonstrate that the average behavior of a particular vocal function measure deviates by at least 1 standard deviation from normative values.

Throughout the first voice therapy session, the VHM will be worn with the goal of establishing a significant change in a voiced feature associated with perceptually improved voicing per the SLP. The SLP will use the VHM's real-time summary feedback to assess if improved voicing is significantly different than baseline. First, the baseline threshold will be based on 85th and/or 15th percentiles of measures from baseline that were >1 standard deviation away from our normative database. Second, the improved voicing must be over 90% compliant for at least 1 feature.

During the first therapy session, once the clinician has established that the patient can modify their voicing the patient will qualify for ambulatory monitoring without AVB the following week. Of note, patients will have already been trained on VHM use without AVB in the 2011P002376 protocol and completed a week of monitoring. After the first voice therapy session, each patient will begin monitoring without AVB in daily life. There will be no feedback in the patient's daily life so that we can evaluate if the patient can improve their voicing outside the therapy session without feedback.

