The patient will receive monitoring with AVB during their second voice therapy session and subsequent monitoring in daily life. Starting in the second therapy session, the SLP will review the patient's performance over the previous week. The patient will be trained on using, and begin receiving, feedback for the last half of their therapy session. The training will include presenting how the biofeedback parameter is affected by their success. The patient will be asked to produce the targeted vocal behavior using negative practice in which s/he will be asked to purposefully perform a voicing task correctly and incorrectly to experience biofeedback cueing. The AVB will be provided throughout the second half of the first therapy session so that the patient can have practical training on its use and the clinician can ensure the AVB is tracking with improved voicing appropriately. During the ambulatory voice recordings, the patient will receive feedback on all 4 days of monitoring. During the week that the patient receives feedback, starting after this second therapy session, [name] will set up the VHM to provide feedback.

Starting in the third therapy session, the SLP will review the patient's performance over the previous week. If the patient did not respond to the feedback during week 2 monitoring, the study will stop for the patient and they will be paid for two voice therapy sessions and 8 days of monitoring (4 days per week). If the patient did respond to the feedback, they will qualify to continue the study during their third therapy session and in daily life the following week. The patient will be monitored during the third therapy session and for 4 days the subsequent week without the feedback. The purpose of the third week of monitoring is to see if the patient can retain their vocal improvements without the feedback.

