Day 2 and Day 3 recording without feedback will be two consecutive days post-Day1. Wear VHM until record 40 minutes of voicing

Day 4 recording without feedback will be the day before Week 2's voice therapy session. Wear VHM until record 40 minutes of voicing.

Statistical Analysis Plan:

Study Two will use one repeated measure ANOVA with 3 levels (pre-therapy days, AVB days pooled together (therapy week 2), retention days pooled together (after stopping AVB, therapy week 3) for the outcome variable of overall percentage compliance. The finding of interest is the main effect of "Level." Appropriate post hoc tests will be conducted on the main effects (if significance is achieved). It is hypothesized that the ANOVA will show, compared to pre-therapy, a significantly increased percentage compliance for all other levels. This result will demonstrate the expected large AVB effect that fades after AVB removal (smaller improvements during retention days than AVB days).

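### The only planned analysis leaves out week 1 (therapy without AVB) and compares with pre-therapy, so a significant result would not by itself show an AVB effect

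*Combined protocol and SAP*

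**What the plan says.** The Study Protocol section and Table II describe four phases per patient: about a week of pre-therapy monitoring, week 1 (after therapy session 1, no AVB), week 2 (after session 2, AVB on all four recording days) and week 3 (after session 3, AVB withdrawn). Week 1 has its own stated purpose: it is recorded "so that we can evaluate if the patient can improve their voicing outside the therapy session without feedback".

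The Statistical Analysis Plan section uses only three of these phases: "Study Two will use one repeated measure ANOVA with 3 levels (pre-therapy days, AVB days pooled together (therapy week 2), retention days pooled together". On the test itself it says "The finding of interest is the main effect of" Level. Follow-up tests are left open: "Appropriate post hoc tests will be conducted on the main effects (if significance is achieved"). The hypothesis is higher percentage compliance than pre-therapy at the other levels, and the inference drawn is: "This result will demonstrate the expected large AVB effect that fades after AVB removal (smaller improvements during retention days than AVB days").

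Two further statements in the Study Protocol section bear on this. On continuation to week 3: "If the patient did not respond to the feedback during week 2 monitoring, the study will stop for the patient". On when AVB is first used in the clinic: "The AVB will be provided throughout the second half of the first therapy session", whereas the rest of the section and Table II introduce AVB in the second session.

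**The concern.** The change from pre-therapy to week 2 contains AVB, two voice therapy sessions and elapsed time. Improvement from therapy alone is expected by design, since a patient enters week 1 monitoring only after showing in session 1 that the voice can be modified. Effective therapy with useless biofeedback would therefore give a significant Level effect, and the plan would report it as an AVB effect.

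The AVB-to-retention comparison looks like an on/off contrast that could separate the two. It is not named as a test. Week 3 also follows AVB exposure and a third session, and it is observed only in patients judged to have responded in week 2. Keeping patients because week 2 was good makes week 3 look worse through regression to the mean.

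Week 1 is the one phase with therapy and no AVB that comes before AVB and is not filtered on response to it. The analysis does not use it.

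**Working it through.** **The plan's own figure.** The sample size is "48 total patients (20 with phonotraumatic VH and 20 with non-phonotraumatic VH + potential 20% drop out rate"). 40 × 1.20 = 48 reproduces it; dividing instead gives 40 / 0.80 = 50. A 20% loss from 48 leaves 48 × 0.80 = 38.4, so I use n = 40. The documents give no alpha, power, effect size, SD, within-patient correlation or definition of response.

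**Assumptions (not in the documents).** Two-sided alpha 0.05; true AVB effect zero; therapy alone raises weeks 1, 2 and 3 equally by d; independent normal phase errors with SD 1/√2, so a paired change has SD 1 and d is in those units.

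**1. Comparison with pre-therapy.** The paired t test has 39 degrees of freedom and noncentrality d√n. For d = 0.5 this is 0.5 × √40 = 3.16. The Level test was simulated with week 3 available for all 40 (6,000 runs).

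| Therapy-only shift d | Week 2 vs pre-therapy, 0.05 | Same, Bonferroni 0.05/3 | Planned Level test |
|---|---|---|---|
| 0.2 | 23% | 12% | 25% |
| 0.3 | 46% | 29% | 47% |
| 0.5 | 87% | 74% | 90% |
| 0.8 | over 99% | 99% | over 99% |

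Every entry is the chance of a significant result with no AVB effect. A separate simulation expressed the shift in SDs of the outcome and let the within-patient correlation run from 0.3 to 0.7. The Level test was significant in 37–69% of trials at 0.3 SD, 78–99% at 0.5 SD and 99.6–100% at 0.8 SD.

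**2. The fade (week 2 above week 3, p < 0.05), still with no AVB effect (20,000 runs).**

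- No selection: about 2.5% in that direction.
- Response means week 2 above week 1: about 20 of 40 are kept. The expected value of the larger of two independent normals exceeds their mean by SD/√π = 0.707/1.772 = 0.40, so a fade of 0.40 SD appears from selection alone. It is significant in about 45% of runs.
- Response means week 2 above pre-therapy: 23 to 32 are kept, and the fade is significant in 39%, 35%, 27% and 18% of runs at d = 0.2, 0.3, 0.5 and 0.8.
- Milder selection, best 40 of 48 on the week 1 to week 2 gain: about 16%, or 8% with Bonferroni.

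Selection also affects the planned test. A repeated-measures ANOVA in its usual form needs all three levels, so it would run in responders only. With the 70% of patients who gained most from week 1 to week 2 kept (correlation 0.5), no therapy effect and no AVB effect, the Level test was significant in 26% of runs, against 5% without selection.

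**3. Week 2 minus week 1.**

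- All patients with both weeks: about 5%.
- Responders only: about 100% under the first response rule and 18–38% under the second.
- Four-level random-intercept mixed model with week 3 missing for non-responders (300 runs per rule, d = 0.3): 4.7% and 4.3%, with mean estimates 0.009 and −0.005.

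**The case against.** The strongest reply is that the plan predicts more than a rise from pre-therapy. It also predicts smaller gains once AVB is withdrawn, and cumulative therapy benefit would not produce that. This would carry weight if everyone supplied week 3 data, but non-responders stop.

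One can also say that the 45% fade rate comes from a harsh response rule that discards half the patients, and that the fade alone is not the full predicted pattern. Both points are fair. Suppose the Level test, both comparisons with pre-therapy and the fade must all be significant. Under the week 2 above week 1 rule the joint rate is then about 3%, 6%, 18% and 38% at d = 0.2, 0.3, 0.5 and 0.8, and with Bonferroni 0.4%, 1%, 6% and 19%. Under the other rule it is 18–26%, or 6–11% with Bonferroni. The plan does not, however, require the fade to be significant. If a numerically smaller gain in retention is enough, the joint rate in responders is about 12% to 90%, depending on d and the rule.

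Three further points stand as limits:

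- The order is fixed and there is no control group, so week 2 minus week 1 still contains session 2 and time. The 5% figure assumes that therapy benefit does not grow after session 1.
- Week 1 is used clinically, since the therapist reviews it at session 2. It is missing only from the statistical analysis. It is also restricted to patients who could modify their voicing in session 1.
- If AVB really was given in session 1, week 1 would not be free of prior AVB exposure, so that contradiction must be settled before week 1 serves as the comparator.

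The protocol's single-subject framing does not help, because no single-subject analysis is specified.

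**Conclusion.** The concern holds. Followed exactly, the plan would attribute to AVB a change that therapy alone can produce. The confounding follows from the documents and needs no numerical assumption; only its size does. With 40 patients, no AVB effect and a therapy-only shift of 0.2 to 0.8 SD of the paired change, the Level test is significant in 25% to over 99% of trials. The spurious fade depends on an undefined response rule and ranges from about 16% to 45% over the rules tried, or lower if corrected for multiplicity, so the 45% should be read as an upper example. Because this is the only planned analysis and it carries the study's central claim, it must be corrected before the results are interpreted.

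**What to change.** Amend the Statistical Analysis Plan as follows:

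- Add week 1 as a level and name week 2 minus week 1 as the primary AVB contrast.
- Estimate it in every patient with week 1 and week 2 data, whatever their response and whether or not they have week 3 data. Use a paired test or a mixed model on all available data, not a complete-case four-level ANOVA.
- State the alpha and the multiplicity method for the remaining contrasts.
- Describe comparisons with pre-therapy as therapy plus AVB combined.
- Label any contrast that uses week 3 as secondary, limited to responders, and subject to selection and carryover.
- First reconcile the Study Protocol sentence that places AVB in the first therapy session with the passages and Table II that start it in the second.

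The cost is wording: week 1 recording is already scheduled. With 40 patients the paired contrast has about 80% power at 0.45 SD of the paired change and over 99% at 0.8 SD. The AVB effect will probably look smaller than it would against pre-therapy. The new contrast reduces the confounding but does not remove it. If session 2 and time alone add 0.1, 0.2 or 0.3 SD, it is significant in about 9%, 23% or 46% of trials with no AVB effect, and the report should state this limit.

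### Recruitment is set by diagnosis, but the planned ANOVA has no diagnosis term and gives no estimate by diagnosis, so a Level effect arising in one group could be read as applying to both.

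*Combined protocol and SAP*

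**What the plan says.** The opening paragraph of the Study Protocol gives the sample as "48 total patients (20 with phonotraumatic VH and 20 with non-phonotraumatic VH + potential 20% drop out rate"). Diagnosis is the only patient characteristic with its own recruitment number. The same paragraph describes each patient as "each handled as a single subject design to test if large changes in voicing occur during AVB", and gives the purpose as follows: "we aim to demonstrate improvement with AVB across subjects who will have different measures as biofeedback targets".

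The Statistical Analysis Plan is one paragraph. It states that "Study Two will use one repeated measure ANOVA with 3 levels": pre-therapy, AVB (therapy week 2) and retention (therapy week 3). The outcome is percentage compliance. It continues "The finding of interest is the main effect of" Level, and adds: "Appropriate post hoc tests will be conducted on the main effects (if significance is achieved"). The paragraph contains no diagnosis factor, diagnosis-by-Level interaction, stratified analysis or summary by diagnosis. The single-subject description has no matching per-patient analysis.

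**The concern.** The one structural feature of the sample plays no part in the analysis. A pooled Level effect averages over the two diagnoses. It cannot show whether both improved or one improved enough to carry the average. The stated purpose is improvement across patients with differing targets, so a reader of a significant result could easily take it to cover both types of vocal hyperfunction. The planned output would contain nothing to confirm or correct that reading.

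There is a smaller cost in precision. If the gain differs between diagnoses, a model without diagnosis puts that difference into the Level-by-patient error term.

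**Working it through.** **The plan's own figure.** 20 + 20 = 40, and 40 × 1.2 = 48, which is the stated enrolment. The 20 per group cannot be re-derived, because no alpha, power, SD or effect size is given.

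**Assumptions.** Two-sided alpha 0.05; compound symmetry; complete data at all three levels; retention gain half the AVB gain; an effect in one diagnosis and exactly zero in the other. The effect is in SD units of within-patient change (AVB minus pre-therapy). The Statistical Analysis Plan expects a large effect without a number, so I show 0.5 to 1.2 SD.

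**How often the pooled Level test is significant when one diagnosis alone responds** (simulation, 20,000 or more trials per setting):

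| Effect in the responding group (SD) | Level F test, 20 + 20 | F test plus Bonferroni AVB vs pre-therapy | Level F test, 16 + 16 |
|---|---|---|---|
| 0 (no effect in either) | 5% | 1% | 5% |
| 0.5 | 25% | 16% | 20% |
| 0.8 | 56–57% | 44% | 45% |
| 1.0 | 75% | 64% | 64% |
| 1.2 | 89% | 80% | 79% |

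The third column is one way to carry out the post hoc step, since the plan does not name the test.

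**Precision of the pooled contrast.** Let the change have SD σ within each diagnosis and let the group means differ by δσ. With equal groups the pooled variance of change is σ²(1 + δ²/4), so the standard error is inflated by √(1 + δ²/4).
- δ = 1: √1.25 = 1.118, about 12%.
- δ = 1.5: √1.5625 = 1.25, or 25%.

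**Cost of adding diagnosis.** Error df fall from (40 − 1) × 2 = 78 to (40 − 2) × 2 = 76. I assume a patient SD of 6 points and a residual SD of 8 points:
- Gains of 10 and 0 points: power for Level is about 65% without diagnosis and about 69% with it.
- Gains of 5 and 5 points: about 69% and 69%.

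**What the added estimates can show.** The 95% CI half-width for the difference between diagnoses is t × √(2/n) in SD units.
- 20 per group: 2.024 × √(2/20) = 0.64 SD.
- 16 per group: 2.042 × √(2/16) = 0.72 SD.
- 12 per group: 2.074 × √(2/12) = 0.85 SD.

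When one group alone responds, the diagnosis-by-Level test with 20 per group has power of about 27%, 60%, 80% and 93% at 0.5, 0.8, 1.0 and 1.2 SD. A paired test within the responding group has power of 56%, 92%, 99% and over 99%. The per-diagnosis contrasts are therefore informative for large effects, while the interaction test is weak at 0.8 SD and below.

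**The case against.** The strongest reply is that the planned test is not wrong. A main effect of Level is a valid test of the average effect, the aim is worded across patients, and the plan states no hypothesis about diagnosis. Equal recruitment may only be a quota to obtain a mixed sample, and a quota does not by itself require an interaction test. The official title also calls these preliminary studies. All of this stands, and it makes the point one of missing estimates rather than an invalid test.

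A reader might infer that the sponsor will report a one-group effect as an effect in both diagnoses. The documents do not support that: no sentence promises a claim by diagnosis. What they leave open is that a significant result could be read that way, with no planned output to check it.

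A reader might also expect the fix to make a Level result driven by one group less likely. It does not. In the 10 versus 0 point case it makes such a result slightly more likely (about 69% against 65%). The protection comes from the per-diagnosis contrasts and the estimated difference.

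A two-level paired calculation for the AVB contrast alone at n = 40 gives 63%, 79% and 89% at 0.8, 1.0 and 1.2 SD. The first two are too high for the three-level F test that is planned.

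Finally, the calculations keep every patient, while the Study Protocol stops week 2 non-responders before the retention week. If the ANOVA uses complete cases, which is not stated, a poorly responding diagnosis would lose more patients and the unweighted mean would move towards the other. Equal weighting restores the diagnosis mix. It does not undo selection on response within each diagnosis, which is a separate issue.

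**Conclusion.** The concern holds in a limited form. The omission is plain from the text and does not depend on any assumed number: the sample is built on diagnosis, and the analysis yields no estimate by diagnosis. The pooled test remains valid for the average effect.

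Under the stated assumptions, for effects of 0.8 SD or more in one diagnosis only, the planned F test would be significant in more than half of trials. Those percentages are illustrative and fall with fewer complete patients. The loss of precision is modest. The change should be made because it costs almost nothing and supplies what is needed to judge how widely the result applies.

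**What to change.** In the Statistical Analysis Plan:

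1. Add diagnosis as a between-subject factor with a diagnosis-by-Level term. The recruitment targets are set by diagnosis, so it is known for each patient at enrolment.
2. Test Level as the equally weighted average over the two diagnoses, so that unequal losses do not change the mix.
3. Report the AVB versus pre-therapy and retention versus pre-therapy contrasts, each with a 95% CI, for each diagnosis and for the difference between them. That is 2 × 3 = 6 intervals.
4. Label the difference between diagnoses as estimation, and state that a non-significant interaction will not be read as equal effects. Say whether the six intervals are descriptive or adjusted for multiplicity.

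The cost is 2 error df and a few more reported contrasts. No extra patients, visits or measurements are needed. How patients stopped after week 2 enter the analysis must be settled separately.

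### The SAP draws a conclusion of fading after AVB removal without making it depend on a test of week 3 against week 2

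*Combined protocol and SAP*

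**What the plan says.** The Statistical Analysis Plan opens: "Study Two will use one repeated measure ANOVA with 3 levels". The levels are pre-therapy, week 2 (AVB on) and week 3 (AVB off), and the outcome is overall percentage compliance. The main effect of Level is the declared finding of interest. On follow-up tests it says only: "Appropriate post hoc tests will be conducted on the main effects (if significance is achieved". No pairs, direction or multiplicity method are given.

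The hypothesis is: "It is hypothesized that the ANOVA will show, compared to pre-therapy, a significantly increased percentage compliance for all other levels". The next sentence draws the conclusion: "This result will demonstrate the expected large AVB effect that fades after AVB removal (smaller improvements during retention days than AVB days".

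Two statements in the Study Protocol bear on this. Week 3 has its own aim: "The purpose of the third week of monitoring is to see if the patient can retain their vocal improvements without the feedback". Not every patient reaches it: "If the patient did not respond to the feedback during week 2 monitoring, the study will stop for the patient". What counts as a response is not defined.

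**The concern.** The hypothesised result consists of two comparisons, week 2 with pre-therapy and week 3 with pre-therapy. The conclusion concerns a third, week 3 with week 2. Both increases can be significant when the effect fades, when it is fully retained, or when it grows further. Whether improvement is retained or fades is what week 3 can tell the reader, and the SAP has no rule that separates the two. A report that follows the SAP could state that the effect fades when week 3 is lower only by chance, or lower because patients were selected on a good week 2.

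**Working it through.** **The plan's own figure.** The Study Protocol gives "48 total patients (20 with phonotraumatic VH and 20 with non-phonotraumatic VH + potential 20% drop out rate". 20 + 20 = 40, and 40 × 1.2 = 48, so the figure reproduces. It is used here only to set the numbers of patients. The documents give no alpha, SD, effect size, correlation or response rate, so everything below is assumed and shown over a range.

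**Step 1: model.** Each patient has a week 2 gain and a week 3 gain over pre-therapy. The gains are normal with SD 1 and correlation r = 0.3, 0.5 or 0.7. There are 40 patients and 20,000 simulated trials per setting. The gate is the repeated-measures F test of Level at 0.05. Paired tests use t = mean(d) / (SD(d)/√n), two-sided at 0.05.

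**Step 2: no true fade (equal mean gains), no selection.**

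| Rule for claiming fading | Gain 0.5 SD | Gain 0.8 SD |
|---|---|---|
| Both increases significant, parenthesis ignored | 76–80% | over 99% |
| Both significant and week 3 mean numerically lower | 38–40% | 50% |
| Gate plus significant Holm-adjusted week 3 minus week 2 contrast | 1.5–1.8% | 2.4% |

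The second row follows from the first by symmetry. With equal true means, week 3 falls below week 2 half the time: 0.76 × 0.5 = 0.38, 0.80 × 0.5 = 0.40, and 1.00 × 0.5 = 0.50. If week 3 is truly 25% better than week 2, the second rule still claims fading in 14–22% of trials (0.5 SD) or 5–15% (0.8 SD).

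**Step 3: selection on week 2.** Suppose 48 patients enrol and those with the k lowest week 2 gains stop, with no true fade. Keeping the upper part of a normal distribution raises the retained week 2 mean by about φ(z)/(1 − p), where p = k/48.

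- k = 4: p = 0.083, z = −1.38, shift = 0.153/0.917 = 0.17 SD.
- k = 8: p = 0.167, z = −0.97, shift = 0.250/0.833 = 0.30 SD.

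Week 3 keeps only the fraction r of that shift, so the expected spurious change is −(1 − r) × shift. At r = 0.5 this is about −0.08 and −0.15 SD.

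Simulated false-fading rates over both gains and all three correlations:

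- Gate plus Holm-adjusted contrast: 6–10% for k = 4 and 11–22% for k = 8.
- Both increases significant and week 3 numerically lower: 65–87% across k = 4 and 8.

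**Step 4: a model that keeps the stopped patients.** A likelihood-based model using everyone's pre-therapy, week 1 and week 2 data plus the available week 3 data was simulated with compound-symmetric correlation (4,000 trials). Its bias was within 0.004 and its false-fade rate 2.3–2.7%. In that simulation stopping depended only on recorded compliance, which favours the model.

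**Step 5: power of the contrast.** For n = 40 and an assumed standardised paired difference (dz) of 0.45, the noncentrality is 0.45 × √40 = 2.85. Power is 79% at 0.05 and 64% at 0.05/3, Holm's strictest step. At a gain of 0.8 SD without selection, the Holm rule detects a 25% fade in 17–35% of trials and a 50% fade in 51–87%.

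**The case against.** The best defence is that the parenthesis already states the ordering, and that post hoc tests on a three-level factor ordinarily mean the three pairwise comparisons. This largely stands. A reader might infer that the SAP would claim fading from the two baseline comparisons alone, wrongly in 76% to over 99% of trials. The documents do not support that as the natural reading, because it ignores the parenthesis.

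A reader might also infer that the named result is less likely under fading than under full retention. That too needs the most literal reading. Once the ordering counts, the result is more likely under a 25% fade than under none: 81–91% against about 50% at 0.8 SD. At 0.5 SD the rule discriminates poorly, 40–51% against 38–40%.

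It is also fair that fading is only an expected pattern in a study titled as preliminary, and that the declared target is the main effect of Level. Nothing here touches that test or the comparisons with pre-therapy, and week 3 against pre-therapy does speak to retention.

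Finally, the 2% figure must not be offered as what the fix achieves in this design, because it assumes no selection. The 6–22% range in turn rests on an assumed stopping rule and assumed numbers stopped. It shows how far selection could matter, not that it will matter that much.

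What survives is that the contrast is not named, no criterion for fading is given, and the conclusion is worded as following from the comparisons with pre-therapy.

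**Conclusion.** The point holds in a narrow form. The conclusion of fading does not follow from the evidence the SAP attaches to it, and this needs none of the assumed figures. On the fairer reading, where a numerically lower week 3 mean is enough, a false claim of fading would arise in about 38–50% of trials without selection, and in 65–87% if 4 to 8 of 48 patients stop on low week 2 gains. A tested contrast lowers these to about 2% and 6–22% respectively, so it reduces the error without removing it. The sizes rest on normal gains with SD 1, mean gains of 0.5 or 0.8 SD, correlation 0.3 to 0.7, two-sided 0.05, and stopping of exactly the lowest week 2 gains. Severity is minor to moderate: the wording should be changed before analysis, but the main test stands.

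**What to change.** Replace the last sentence of the Statistical Analysis Plan with text such as:

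> If the main effect of Level is significant, three paired contrasts are pre-specified: week 2 minus pre-therapy, week 3 minus pre-therapy, and week 3 minus week 2, with multiplicity-adjusted (for example Holm) p-values and 95% confidence intervals. Increases over pre-therapy support only improvement in the week concerned. A decline from week 2 to week 3 will be reported only if week 3 minus week 2 is significantly below zero. It will be described as a decline among week 2 responders, part of which may be regression to the mean because patients were selected on week 2. A non-significant contrast is not proof of retention. Fading in all patients will not be concluded from this contrast alone.

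Beside it, report as a sensitivity analysis the week 3 minus week 2 estimate and 95% confidence interval from the mixed model in step 4. State that it targets all patients and assumes stopping depends only on recorded compliance.

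The cost is SAP wording and one extra model. No new data are needed, provided the records of patients stopped after week 2 are kept. The adjustment costs power, from 79% to 64% at worst in the example above, and small fades will often stay unproven. The estimate and interval should therefore be reported whatever the test shows. Holm is one acceptable choice; the essential change is that the claim depends on the named contrast.

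### The SAP treats significant increases over pre-therapy as proof of a large biofeedback effect, but significance only excludes zero and the plan sets no criterion for size

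*Combined protocol and SAP*

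**What the plan says.** The opening paragraph of the Study Protocol describes single-subject designs whose purpose is "to test if large changes in voicing occur during AVB (acquisition) and the days post-AVB (retention". It plans "48 total patients (20 with phonotraumatic VH and 20 with non-phonotraumatic VH + potential 20% drop out rate".

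The Statistical Analysis Plan then specifies a group analysis: "Study Two will use one repeated measure ANOVA with 3 levels" (pre-therapy, AVB in week 2, retention in week 3), "for the outcome variable of overall percentage compliance". The main effect of level is tested, and post hoc tests follow if it is significant. The hypothesis is stated thus: "It is hypothesized that the ANOVA will show, compared to pre-therapy, a significantly increased percentage compliance for all other levels". The next sentence gives the interpretation: "This result will demonstrate the expected large AVB effect". It adds that the effect fades once AVB is removed, with smaller gains in retention than during AVB.

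Neither part defines large, gives a minimum gain in compliance, names an effect-size measure or asks for a confidence interval. The remark about smaller gains in retention concerns the order of the levels and says nothing about how big either gain is.

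**The concern.** The conclusion is about size, but the evidence named for it is a set of significance tests. A significant difference from pre-therapy shows that the mean change is unlikely to be zero. It does not separate a small or moderate gain from a large one. How small a gain can reach significance depends on the number of patients, so what earns the word large is set by the sample size and not by any judgement about voice function.

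At stake is what the trial may conclude. If the SAP is followed as written, a moderate gain that reaches significance in both weeks would be reported as a demonstrated large AVB effect, and nothing in the plan would show the reader otherwise.

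**Working it through.** **Inputs from the documents.** 20 + 20 = 40 patients before the dropout allowance; three levels; one outcome, overall percentage compliance; significance against pre-therapy required at both other levels.

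**Inputs not given, so assumed.** Two-sided 5%. The post hoc method is unstated, so results run from unadjusted to Bonferroni over three comparisons (0.05/3 = 0.0167). The SD of change in compliance is unstated, so results are in SDs of the change scores, with points shown for a range of SDs. The number of patients with all three levels is unstated. It may be below 40 because the protocol ends participation for those who do not respond in week 2, so 20 to 40 is shown.

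**The plan's own figure.** 40 × 1.2 = 48, which reproduces the stated total. The 40 itself cannot be derived, since no effect size, alpha or power is given. The sample size therefore offers no implied definition of large either.

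**Step 1: smallest observed change that is significant.** For a paired comparison, d = t(1 − α/2, n − 1)/√n.

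| Complete patients | Unadjusted | Bonferroni over 3 |
|---|---|---|
| 40 | 2.023/6.325 = 0.32 | 2.502/6.325 = 0.40 |
| 30 | 2.045/5.477 = 0.37 | 2.541/5.477 = 0.46 |
| 20 | 2.093/4.472 = 0.47 | 2.625/4.472 = 0.59 |

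With 40 patients, if the SD of change were 10, 20 or 30 points, the thresholds would be 3.2, 6.4 or 9.6 points unadjusted, and 4.0, 7.9 or 11.9 points with Bonferroni.

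The omnibus test, assuming sphericity, is significant from F(2,78) = 3.114. That is a partial eta-squared of 2 × 3.114/(2 × 3.114 + 78) = 0.074.

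At the threshold the observed change equals the margin of error, so the unadjusted lower 95% limit is 0.32 − 0.32 = 0. Such a result is compatible with almost no effect.

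**Step 2: how often the full result occurs.** The SAP's sentence rests on the omnibus test and both comparisons with pre-therapy being significant in the right direction. This was simulated with 40 patients, normal data and a correlation of 0.5 between levels (assumed). True changes are in SDs of the change scores.

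| True change, AVB / retention | Unadjusted | Bonferroni over 3 |
|---|---|---|
| 0.3 / 0.3 | 28% | 14% |
| 0.5 / 0.3 | 44% | 26% |
| 0.5 / 0.5 | 78% | 61% |

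With 20 complete patients, 0.5 / 0.5 gives 38% and 21%. The simulation does not model the selection caused by stopping week-2 non-responders. That selection keeps patients who improved under AVB, so it would make a significant AVB increase easier to obtain.

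**The case against.** **A higher bar than one test.** A reader might infer that any significant increase would be called large, or that a true change of 0.3 SD would be so labelled 46% of the time and 0.5 SD 87% of the time. Those figures are the power of a single unadjusted paired comparison with 40 patients. The SAP ties its sentence to significance at all other levels, after the omnibus test, so the figures that apply are the lower ones in the second table. The chance of a misplaced claim falls further if fewer than 40 patients have complete data or the post hoc tests are adjusted. This stands and limits the size of the problem. It does not repair the inference, because the full pattern still carries no information about a minimum size.

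**An expectation, in preliminary work.** The sentence follows a hypothesis and calls the effect expected. Nothing forbids reporting estimates. That is fair, but the sentence also says what the result will be taken to demonstrate, and it is the only rule of interpretation in the SAP.

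**A patient-level aim.** The protocol speaks of large changes within single-subject designs. A reader might infer that the ANOVA was meant to answer that question and answers it wrongly. The documents do not go that far. The point here rests on the SAP attaching the word large to its own group result.

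**Conventions.** Reading 0.8 SD as large is a convention that the documents do not adopt. A reader might also infer that the lower confidence limit must exceed whatever counts as large. That is one possible standard and a demanding one. With 40 patients and a margin of 0.8 SD fixed in points, the observed change would have to exceed about 0.80 + 0.32 = 1.12 SD, and a true change of 1.0 SD would pass only 23% of the time. The documents do not oblige the sponsor to adopt it.

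**Conclusion.** The concern holds in this form: the SAP draws a conclusion about size from tests that address only whether the change is zero, and no size criterion appears anywhere in the documents. That part needs no assumption.

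Its scale rests on two-sided 5% tests and, for the simulation, on a correlation of 0.5 and 40 complete patients. On those terms, changes of 0.32 to 0.40 SD reach significance, and a moderate true effect meets the full pattern between about a quarter of the time (0.5 SD fading to 0.3, Bonferroni) and just over three quarters (0.5 SD at both levels, unadjusted). Even with 20 complete patients the threshold of 0.47 to 0.59 SD stays below the conventional 0.8. The points figures are illustrative because the SD of change is not given.

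The ANOVA as a test for any increase is not in question here, and neither is the claim about fading.

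**What to change.** Replace the interpretive sentence in the Statistical Analysis Plan with wording to this effect:

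- Significant differences from pre-therapy support the conclusion that compliance increased, and no more.
- AVB minus pre-therapy and retention minus pre-therapy are each reported in percentage points with a 95% confidence interval.
- Before analysis, the sponsor states the gain in points that it regards as large. Any statement that the effect is large rests on the estimates and intervals set against that gain.

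Whether the lower confidence limit must exceed the stated gain, or a less strict reading of estimate and interval suffices, is the sponsor's choice. It should be written down with the gain.

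The cost is SAP wording and one decision about size; data collection does not change. The downside for the sponsor is that large is no longer earned by significance alone. If the strict lower-limit rule is chosen, 40 patients may not be enough to meet it unless the true gain is well above the stated one.
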